10 STUDY PROCEDURES

This is an approximately 28-week outpatient study. Screening procedures will be performed as a virtual visit followed by a Homecare in-person visit. Eligible and consenting patients will be randomized to an approach group at telephone Visit 2-Step 1, which will determine the way the next visits are organized:

- Traditional group: 5 onsite visits and 7 telephone visits
- Virtual group: 11 virtual visits and 1 mixed onsite-virtual visit (Visit 2-Step 2)

Additional, optional virtual or telephone visits (according to the approach group) will be scheduled to monitor and support the progress of insulin titration whenever considered necessary by the investigator. For both groups, unscheduled onsite visits or Homecare physician visits (depending on the patient's location) may be scheduled only for safety assessment if deemed necessary by the investigator (ie, performance of physical examinations is critical to determine a diagnosis or further evaluation procedure for an AE).

All onsite visits should take place in the morning at approximately the same time. On the day before each onsite visit, patients should be reminded to bring the medical devices (glucose meter), diaries and IMP (used, in-use or unused) to sites and to be in the fasted status if required at some visits.

The **fasting condition** is defined as an overnight fast no less than 8 hours that consisted of no food or liquid intake, other than water. IMP and noninsulin antidiabetic medication should be administered after the fasting blood sample is drawn for all laboratory tests.

Note: If the patient is not in fasting conditions at visits which required in fasting conditions, the blood sample is not collected and a new appointment should be given to the patient for the following day if possible, with instruction to be fasted.

For phone-call visits and virtual visits, the patient is called by the investigator or qualified designee at a scheduled time.

A visit window of ± 3 days using the day of Visit 2-Step 2 as reference is acceptable (4 days for Visit 6, Visit 8, and Visit 10).

If one visit date is changed, the next visit should take place according to the original schedule, ie, counting from Day 1 on Visit 2-Step 2.

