2.1.7.3 Study methodology endpoints: Patient burden with trial participation (OSEP)

Patient burden with trial participation will be measured using a new PRO: the Overall Study Experience-Participation (OSEP) Questionnaire. Each item will be scored separately. The OSEP has 2 parts:

- OSEP Part 1 contains 4 items to examine perceptions of diabetes control; it will be administered at baseline and Week 24 (Visit 12).
- OSEP Part 2 contains 9 items to examine perceptions of study participation; it will be administered only at Week 24 (Visit 12).

See questionnaire in [Appendix E](#).

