2.1.8 Investigator (clinician) reported outcome (ClinRO) endpoints

Overall Study Experience-sites (OSES) questionnaire

Site investigators (one per site) will be asked to complete the Overall Study Experience-sites (OSES) questionnaire. The OSES has 2 parts:

- OSES Part 1 contains 1 item to examine resource requirements: "Approximately how much time did you spend with this participant (in person or via phone) during this scheduled visit/communication?". OSES Part 1 will be administered following each study visit.
- OSES Part 2 contains 2 items to examine relationship ("I had a good relationship with this patient during the study") and satisfaction with care ("I am satisfied with the level of care I have provided for this participant in this study"). OSES Part 2 will be administered at Week 24 (Visit 12) only.

Each item is scored separately.

See questionnaire in [Appendix K](#).

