2.5.4 Windows for time points

The following process will be applied for visit re-allocation. Re-allocated visits will be used in all statistical analyses (descriptive statistics, plots, and statistical models).

No re-allocation will be performed for nominal visits already provided in the clinical database (Visit 1 to Visit 20).

SMPG

In the clinical database, SMPG profiles transferred from the e-diary will not be assigned to a protocol visit. For the analysis, they will be assigned to the next visit actually performed by the patient after the date/time of data collection (Visit 3 to Visit 12, or Visit 700).

In the clinical database, SMPG assessments which do not correspond to a 7-point profile transferred from the e-diary will not be assigned to a protocol visit. For the analysis, they will be assigned to the next visit after the date/time of data collection.

Insulin doses

In the clinical database, insulin doses transferred from the e-diary will not be assigned to a protocol visit. For the analysis, they will be assigned to the next on-site visit actually performed by the patient after the date/time of data collection.

PROs and ClinRO

In the clinical database, PROs and ClinRO transferred from the e-diary will not be assigned to a protocol visit. For the analysis, they will be assigned to the video chat/phone call/ on-site visit using the date/time of data collection and the date of first IMP taken (or Randomization date if no IMP taken) as reference for derivation of the Study day .

Table 2 - Reallocation time windows definition

Scheduled visit post baseline	Targeted study day	Analysis window in study days
DTSQs, DDS, HFS-II, WPAI-SP, OSES Part 1		
Day 1 (Visit 2 Step 2)	1	-28 to 1
Week 24 (Visit 12)	169	141 to 196
DTSQc, WIWI, OSES Part 2, OSEP Part 2		
Week 24 (Visit 12)	169	141 to 196
OSES Part 1		
Day 1 (Visit 2 Step 2)	1	-28 to 1
Week 1 (Visit 3)	8	5 to 11
Week 2 (Visit 4)	15	12 to 18
Week 3 (Visit 5)	22	19 to 25
Week 4 (Visit 6)	29	26 to 32
Week 6 (Visit 7)	43	36 to 49
Week 8 (Visit 8)	57	50 to 63
Week 12 (Visit 9)	85	71 to 98
Week 16 (Visit 10)	113	99 to 126
Week 20 (Visit 11)	141	127 to 154
Week 24 (Visit 12)	169	155 to 196

Scheduled visit post baseline	Targeted study day	Analysis window in study days
RUQ		
Day 1 (Visit 2 Step 2)	1	-28 to 1
Week 4 (Visit 6)	29	15 to 42
Week 8 (Visit 8)	57	43 to 70
Week 12 (Visit 9)	85	71 to 98
Week 16 (Visit 10)	113	99 to 126
Week 20 (Visit 11)	141	127 to 154
Week 24 (Visit 12)	169	155 to 196

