2.5.5 Unscheduled visits

The analysis windows mentioned in [Section 2.5.4](#) will be applicable to re-allocate the unscheduled assessments (measurements from the central laboratory only) for HbA1c and FPG assessments.

After applying the time windows as mentioned in [Section 2.5.4](#), if two assessments are associated to the same time point, the closest from the targeted study day is used. In case of equality, the earliest measurement is used.

The determination of baseline for HbA1c and FPG variables is based on all measurements from both scheduled and unscheduled visits (measurements from the central laboratory only). The determination of baseline for safety parameters is based on all assessments from both scheduled and unscheduled visits too. The determination of the last on-treatment value for safety parameters is also based on all assessments from both scheduled and unscheduled visits. Measurements from the unscheduled visits (including results from local laboratory when no corresponding central laboratory results are available) are also considered for PCSA summary of safety parameters.

Unscheduled visit measurements are not included in the by-visit summaries.

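### SAP Table 2 names OSES Part 1 where OSEP Part 1 belongs, and its Week 4 window for OSES Part 1 is narrower than the permitted Visit 6 dates

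*SAP*

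**What the plan says.** SAP 2.5.4 states that PRO and ClinRO records transferred from the e-diary carry no protocol visit. They are assigned from their completion date, in study days counted from first IMP. The same section applies re-allocated visits to every analysis, including descriptive statistics.

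Table 2 has four blocks:

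- Day 1 (-28 to 1) and Week 24 (141 to 196): "DTSQs, DDS, HFS-II, WPAI-SP, OSES Part 1".
- Week 24 only (141 to 196): "DTSQc, WIWI, OSES Part 2, OSEP Part 2".
- OSES Part 1 at Day 1 and every later visit to Week 24, with Week 4 at 26 to 32, Week 20 at 127 to 154 and Week 24 at 155 to 196.
- RUQ.

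OSEP Part 1 is scheduled at baseline and Week 24 (SAP 2.1.7.3 and the Appendix B flowchart). OSES Part 1 has a different schedule: "OSES Part 1 will be administered following each study visit" (SAP 2.1.8).

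On visit timing, Protocol section 10 says "A visit window of ± 3 days using the day of Visit 2-Step 2 as reference is acceptable", and widens this to "4 days for Visit 6, Visit 8, and Visit 10". Protocol 10.1.2.2 lets traditional-group patients take the first dose on the day of Visit 2-Step 2 or on the following day.

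**The concern.** Because these forms have no stored visit label, Table 2 decides which visit each belongs to. An instrument missing from the table cannot be placed. A form dated outside every window drops out of the by-visit tables, and one dated inside a neighbouring window is reported under the wrong visit.

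Two secondary endpoints depend on this. The change in OSEP Part 1 needs both a baseline and a Week 24 value, and SAP 2.5.2 excludes participants with only one of them. OSES Part 1 records site time per visit and is summarized at each visit. Neither should lose data from visits held within the permitted dates.

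**Working it through.** **Which instrument is missing.** None of the four blocks names OSEP Part 1. The first block has exactly its schedule, and OSES Part 1 already has a block covering every visit. Reading OSEP for OSES in the first block gives OSEP Part 1 windows of -28 to 1 and 141 to 196, and leaves OSES Part 1 with one Week 24 window, 155 to 196. One correction therefore removes both the missing window and the duplicate.

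**Size of the duplicate if read literally.** Days 141 to 154 are Week 24 in one block and Week 20 in the other. Visit 11 is permitted on 141 ± 3, i.e. Days 138 to 144, so Days 141 to 144 (4 of 7 dates) qualify for both visits.

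**Windows against permitted dates.** Targeted day = 7 × week + 1. This reproduces all ten OSES Part 1 targets in Table 2: 8, 15, 22, 29, 43, 57, 85, 113, 141 and 169. Permitted study days are the target ± 3, or ± 4 for Visits 6, 8 and 10. If first IMP is the day after Visit 2-Step 2, the same calendar dates fall one study day lower, because visits are counted from Visit 2-Step 2 and study days from first IMP.

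| Visit (week) | OSES window | Permitted, first IMP same day | Misplaced | Permitted, first IMP next day | Misplaced |
|---|---|---|---|---|---|
| 3 (1) | 5–11 | 5–11 | none | 4–10 | 4: no visit |
| 4 (2) | 12–18 | 12–18 | none | 11–17 | 11: Week 1 |
| 5 (3) | 19–25 | 19–25 | none | 18–24 | 18: Week 2 |
| 6 (4) | 26–32 | 25–33 | 25: Week 3; 33: no visit | 24–32 | 24, 25: Week 3 |
| 7 (6) | 36–49 | 40–46 | none | 39–45 | none |
| 8 (8) | 50–63 | 53–61 | none | 52–60 | none |
| 9 (12) | 71–98 | 82–88 | none | 81–87 | none |
| 10 (16) | 99–126 | 109–117 | none | 108–116 | none |
| 11 (20) | 127–154 | 138–144 | none | 137–143 | none |
| 12 (24) | 155–196 | 166–172 | none | 165–171 | none |

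Same-day dosing: 2 of 9 permitted dates at Visit 6 fail and no others. Next-day dosing: 1 of 7 at each of Visits 3, 4 and 5, and 2 of 9 at Visit 6. These are shares of permitted calendar dates, not expected rates of misfiling.

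**Unassigned days.** Between Days 1 and 196 the OSES block leaves Days 2–4, 33–35 and 64–70 without a visit. With same-day dosing, only Day 33 of these is a permitted visit date. Days 64–70 contain none in either case.

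**Would wider windows do?** With same-day dosing, Day 25 is permitted for both Visit 5 (19–25) and Visit 6 (25–33). Allowing either dosing day, the permitted ranges are 4–11, 11–18, 18–25 and 24–33, and each overlaps the next. Date windows alone cannot separate these visits.

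**The case against.** The strongest reply is early termination. SAP section 2 says that the study stopped with 15 patients randomized and that only basic descriptive statistics will be given. The OSEP Part 1 ANCOVA (SAP 2.4.7.3) and the visit-based OSES Part 1 model (SAP 2.4.7.6) will not be run as planned. This stands and limits the consequence to visit labels in tables and listings. It does not remove the point, since SAP 2.5.4 applies Table 2 to descriptive statistics too.

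Several stronger readings are tempting but not supported:

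- *OSEP Part 1 cannot be analyzed.* This follows only from the most literal reading. The block's schedule, and the OSEP Part 1 time points named in SAP 2.5.2, make the intent plain.
- *The Week 20/Week 24 overlap corrupts Week 24.* If the closest form to target is taken, an on-time Visit 12 form (Days 166 to 172) beats one from Days 141 to 144 against the Day 169 target. The overlap then matters only when the Week 24 form is missing.
- *A Day 25 Visit 6 form is discarded in favour of the Visit 5 form.* The rule that "if two assessments are associated to the same time point, the closest from the targeted study day is used" is in SAP 2.5.5, in text framed around central-laboratory HbA1c and FPG. Its use for site questionnaires is an inference. If it does not apply, the SAP does not say which of two Week 3 forms is used.
- *Site time is lost from the resource comparison.* SAP 2.5.2 uses all available data for the on-treatment OSES Part 1 average, and the per-patient total in SAP 2.4.7.6 states no window.
- *The traditional arm is biased.* Next-day dosing is written into that arm's procedure, and flowchart footnote d puts the virtual arm's remaining assessments on the day of first IMP. But Protocol 8.1.5 keeps patients in both arms at their usual injection time, and section 10 also speaks of Day 1 as being on Visit 2-Step 2. No frequencies are given.

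The SAP's provision that nominal visits already in the database are not re-allocated does not help, because these forms are stated to have none.

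**Conclusion.** The point holds as a small, definite error in the visit-assignment rule. First, OSES is written for OSEP in one block; taken literally this leaves OSEP Part 1 unplaced and gives OSES Part 1 two Week 24 windows. Second, and independently, the Week 4 OSES Part 1 window misses two of the nine permitted Visit 6 dates. That needs no assumption beyond same-day first dosing and a form dated on the visit day. With next-day dosing, one date at each of Visits 3, 4 and 5 and two at Visit 6 miss their windows. It would be wrong to infer that the OSES windows are too narrow in general: those from Week 6 on cover every permitted date.

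The effect is confined to by-visit summaries of OSES Part 1 and OSEP Part 1 and any visit-based model. How many forms are affected cannot be derived from the documents. A difference between arms is possible, but its direction and size are unknown.

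**What to change.** Three edits to SAP 2.5.4:

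1. In the first block of Table 2, replace OSES Part 1 with OSEP Part 1.
2. Keep -28 to 1 for baseline OSES Part 1. Protocol 10.1.2.2 lists OSES Part 1 among the traditional-group questionnaires completed in the week before Visit 2-Step 2, so a rule based on the preceding visit would put those forms under an earlier visit.
3. Assign each post-baseline OSES Part 1 form to the latest visit actually performed, by e-CRF visit date, on or before the form's completion date. This separates Visits 5 and 6 at Day 25, and it does not depend on the gap between Visit 2-Step 2 and first IMP.

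The SAP already links SMPG profiles to visits actually performed, so the approach is not new to it. A form completed only after the following visit would still be misfiled; two forms under one visit would flag this for query.

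The cost is one word and one programming rule. It assumes that actual visit dates are in the e-CRF, which Protocol 10.2.1 supports by requiring source documentation of visit dates behind e-CRF entries. Patients and sites do nothing extra.

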- g* EOT assessments will also be performed for any patients who prematurely discontinue the study treatment. Patients should continue the study procedure as planned up to the EOS after IMP discontinuation.
- h* Heart rate and blood pressure (sitting position)
- i* 7-point SMPG profile (before [preinjection after randomization] and 2 hours after breakfast, lunch and dinner, and at bedtime): at least ONE day during the weeks before Visit 2-Step 2 (Week 0), Visit 10 (Week 16), and Visit 12 (Week 24)
5-point SMPG profile (before breakfast, lunch and dinner; 2 hours after a main meal [or as per investigator's instruction] and at bedtime): at least 3 days during the week before each visit
The SMPG before breakfast should be measured in the fasting status, ie, after the patient wakes up, before breakfast, and before injection of any insulin; preferably no food should have been taken overnight. A note should be made in the diary if the SMPG is not tested in fasting status (eg, if food was taken to cope with a hypoglycemic episode)
- j* Only for patients randomized in the traditional group
- k* Blood samples will be sent to and analyzed by Quest® central lab
- l* Hematology: erythrocytes, hemoglobin, hematocrit, leukocytes and platelets. Clinical chemistry: total bilirubin (in case of values above the normal range, differentiation in conjugated and non-conjugated bilirubin), AST, ALT, ALP, plasma glucose, creatinine, estimated creatinine clearance, uric acid, sodium, and potassium
- m* Urine analysis by dipstick: pH, glucose, ketones, leucocytes, blood/hemoglobin, protein
- n* For women of child-bearing potential (WOCBP): serum pregnancy test for screening; urine pregnancy test for subsequent monitoring and it can be confirmed with a serum test if needed. For WOCBP in virtual group, the urine pregnancy test kit will be provided by the study.
- o* For patients randomized to the virtual group, all questionnaires will be performed remotely via the mobile technology at home. For patients randomized in the traditional group, the questionnaires will be completed electronically (via the mobile technology) at the study site (before visiting the study site for baseline assessment on Visit 2 Step 2).
- p* In a subset of patients (approximately 30) in the virtual approach group.

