10.3.5 Procedure and consequence for patient withdrawal from study

The patients may withdraw from the study before study completion if they decide to do so, at any time and irrespective of the reason. Withdrawal of consent for treatment should be distinguished from withdrawal of consent for follow-up visits and from withdrawal of consent for non-patient contact follow-up, eg, medical records check. Patients requesting withdrawal should be informed that withdrawal of consent for follow-up may jeopardize the public health value of the study.

If possible, the patients are assessed using the procedure normally planned for the end-of-study visit.

Patients who withdraw should be explicitly asked about the contribution of possible AEs to their decision to withdraw consent, and any AE information elicited should be documented. Preferably the patient should withdraw consent in writing and, if the patient or the patient's representative refuses or is physically unavailable, the site should document and sign the reason for the patient's failure to withdraw consent in writing.

All study withdrawals should be recorded by the investigator in the appropriate screens of the e-CRF and in the patient's medical records when considered as confirmed. In the medical record, at least the date of the withdrawal and the reason should be documented.

For patients who fail to attend the EOT visit, unless the patient withdraws consent for follow-up, the Investigator should make the best effort to recontact the patient (eg, contact patient's family or private physician, review available registries or health care databases), and to determine his/her health status, including at least his/her vital status. Attempts to contact such patients must be documented in the patient's records (eg, times and dates of attempted telephone contact, receipt for sending a registered letter).

The statistical analysis plan will specify how these patients lost to follow-up for their primary endpoints will be considered.

Patients who have withdrawn from the study cannot be rerandomized (treated) in the study. Their inclusion and treatment numbers must not be reused.

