2.1.7.1 Study methodology endpoints: Patient satisfaction with trial experience (WIWI)

Patient satisfaction with trial experience will be measured using the Was It Worth It (WIWI) Questionnaire, completed at Week 24 (Visit 12). The WIWI has 5 items, each with a 3-level categorical response scale. Each item is scored separately.

See questionnaire in [Appendix C](#).

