Study days are calculated from the day of first IMP, the day of first IMP injection being Day 1. For randomized but not treated patients, Day 1 is the day of randomization.

End of treatment visit

The following analysis windows will be applicable to re-allocate the premature end of treatment assessments (premature EOT visit) for HbA1c and FPG assessments.

Table 3 - Reallocation time windows definition

Scheduled visit post baseline	Targeted study day	Analysis window in study days
HbA1c and FPG		
Week 16 (Visit 10)	113	85 to 140
Week 24 (Visit 12)	169	141 to 196

Study days are calculated from the day of first IMP, the day of first IMP injection being Day 1. For randomized but not treated patients, Day 1 is the day of randomization.

Study days are calculated from the day of first IMP injection; the day of first IMP injection being Day1.

To retrieve all safety and other assessments performed at the end of treatment visit, the following process will be followed: if a patient discontinues the treatment prematurely, end of treatment assessments will be re-allocated to the next scheduled visit for the patient. The next scheduled visit for each patient will be determined as the next visit that should be performed as per protocol, following the last visit actually performed by the patient before end of treatment visit.

For a given parameter, the value will not be re-allocated in the following cases:

- If the parameter is not planned to be collected at the re-allocation visit.
- If a value is already available for the parameter at the re-allocation visit.

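### WIWI, OSEP Part 2 and OSES Part 2 forms completed at a premature end-of-treatment visit have no analysis time point when the patient leaves the study before about Day 141

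*SAP*

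**What the plan says.** Four parts of the plan bear on this.

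- **Collection.** Footnote g of the Protocol 1.2 flow chart states: "EOT assessments will also be performed for any patients who prematurely discontinue the study treatment". Protocol 10.1.5 lists WIWI and OSEP Part 2 (completed by the patient) and OSES Part 2 (completed by the investigator) among the end-of-treatment forms.
- **Planned timing.** All three are scheduled once. SAP 2.1.7.1 has the "Was It Worth It (WIWI) Questionnaire, completed at Week 24 (Visit 12"), and SAP 2.1.7.3 says "OSEP Part 2 contains 9 items to examine perceptions of study participation; it will be administered only at Week 24 (Visit 12"). SAP 2.1.8 gives OSES Part 2 the same single time point.
- **Windows.** SAP 2.5.4, Table 2, groups "DTSQc, WIWI, OSES Part 2, OSEP Part 2" under one window: Week 24, target Day 169, Days 141 to 196. The day count is defined as follows: "Study days are calculated from the day of first IMP, the day of first IMP injection being Day 1". The windows are not confined to the models: "Re-allocated visits will be used in all statistical analyses (descriptive statistics, plots, and statistical models").
- **Premature end of treatment.** The same section moves other end-of-treatment values to the patient's next scheduled visit. One of its two exceptions is "If the parameter is not planned to be collected at the re-allocation visit".

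Against this, SAP 2.4.7 says that the PRO and ClinRO analyses use every available post-baseline value whether or not Toujeo was stopped. SAP 2.5.2 says that the items of these three forms are analysed on all available data without imputation.

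**The concern.** These forms ask whether taking part was worthwhile, how burdensome it was, and how the site saw its relationship with the patient. Someone who leaves early may well answer differently from someone who stays. If the leavers' forms are collected and then left without a time point, each summary describes only patients who were still in the study near Week 20.

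Retention is itself a secondary objective of the comparison. An approach that loses dissatisfied patients could then look as satisfactory as one that keeps them, although the answers showing otherwise are in the database. No other analysis in the SAP recovers them: these forms have no last-available-value analysis, no imputation and no second time point.

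**Working it through.** **1. Reproduce the window.** Day 1 is the first injection, so Week 24 is 24 × 7 + 1 = Day 169, as stated. The lower limit is 20 × 7 + 1 = 141 = 169 − 28, and the upper limit is 169 + 27 = 196. The window therefore opens exactly 20 weeks after Day 1.

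**2. Apply both routes to a premature visit on each of Days 2 to 168** (167 days), with Visits 3 to 12 on nominal Days 8, 15, 22, 29, 43, 57, 85, 113, 141 and 169.

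- Table 2 window: keeps Days 141 to 168, rejects Days 2 to 140.
- Next-visit rule: can place the form only at Visit 12, so Visit 11 must already have taken place. With Visit 11 on Day 141 it keeps forms from Day 142. With the ±3-day visit window the start moves to between Day 139 and Day 145.
- Rejected by both, with visits on nominal days: Days 2 to 140, which is 139 of 167 = 83%.

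Example: a patient stops treatment and leaves on Day 60. The last visit performed is Visit 8 (Day 57) and the next is Visit 9 (Day 85). WIWI is not planned at Visit 9 and Day 60 lies outside Days 141 to 196, so the form has no time point. By comparison, Table 3 gives a premature HbA1c or FPG a place from Day 85.

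**3. Who is affected.** Footnote g and Protocol 10.3.4 keep patients who stop Toujeo in follow-up, as far as possible with a Week 24 visit 24 weeks after randomization. First injection is planned 7 ± 4 days after randomization, so that visit falls on about Day 169 − 11 = 158 to 169 − 3 = 166, inside the window. These patients still contribute a form. The gap concerns those who leave the study.

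**4. How many forms.** The documents give no rate of leaving. Assume that 5%, 10% or 20% leave, that all of them complete the forms at a premature visit, and that the dates are spread evenly:

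| Randomized | 5% | 10% | 20% |
|---|---|---|---|
| 150 (planned) | 7.5 × 139/167 = 6.2 | 15 × 139/167 = 12.5 | 30 × 139/167 = 25.0 |
| 15 (actual) | 0.6 | 1.2 | 2.5 |

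These are forms of each type without a time point.

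**5. Possible effect on a comparison.** This is illustration only. Assume that 80% of stayers and 20% of leavers answer favourably, and that 20% of one group and 5% of the other leave before Day 141.

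- Every leaver completes the form: 0.80 × 0.80 + 0.20 × 0.20 = 68% versus 0.95 × 0.80 + 0.05 × 0.20 = 77%, a difference of 9 points.
- Half of the leavers complete it: (0.64 + 0.02)/0.90 = 73.3% versus (0.76 + 0.005)/0.975 = 78.5%, about 5 points.
- Under the SAP windows: 80% in both groups, difference 0.
- Equal leaving of 10% in both groups, every leaver completing: 0.90 × 0.80 + 0.10 × 0.20 = 74% in each. There is no difference to hide, but the level is shown as 80%.

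**The case against.** The strongest defence is that the window does what the endpoint says. The protocol defines all three measures at Week 24, and a rating given on Day 20 is not the same quantity as one given on Day 169. Redefining the endpoint as an end-of-participation rating would change what is estimated. That stands, and it is why the Week 24 summary should remain.

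A reader might infer that everyone who stops Toujeo early is lost from these summaries. The documents do not support that, because patients off treatment are to stay in the study and attend Week 24.

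A reader might also cite Protocol 10.3.5 as proof that withdrawing patients fill in the forms: "If possible, the patients are assessed using the procedure normally planned for the end-of-study visit". The end-of-study visit is Visit 13, where none of the three is scheduled. The route to a form is footnote g, and a patient who withdraws consent or is lost may leave none.

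The plan gives some protection elsewhere. Study discontinuation and its reasons are reported by group (SAP 2.2), and the protocol adds Kaplan-Meier estimates of withdrawal (11.4.3.1.3), so an approach that loses patients would be visible. That shows who left, but not how they rated the trial.

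Finally, section 2 of the SAP reports early termination with 15 patients randomized instead of 150, and output cut to basic descriptive tables or listings. Early forms might appear in a listing. That lowers the stakes, but the windows still govern any descriptive table.

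**Conclusion.** The point holds for patients who leave the study before about Day 141 and have completed any of these forms at the premature visit. Those forms fall outside both routes in SAP 2.5.4, which conflicts with the all-available-data statements in SAP 2.4.7 and 2.5.2. It also makes the summaries conditional on retention. The cut at Day 141 follows from the SAP's own day count and assumes visits close to their nominal days.

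The size of any distortion is unknown. A reader might take the 9-point example as an estimate of bias, but its inputs are assumptions. It falls to about 5 points if half of the leavers complete the form and to zero between groups if leaving and answers are alike. WIWI is also planned as five separately scored items summarised by means and medians, not as a percentage favourable. With 15 patients, nothing beyond description is possible.

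This is an inexpensive improvement to secondary endpoints. It does not touch HbA1c. DTSQc shares the same window, but it rates change in treatment satisfaction rather than the trial experience, and no change is asked for there.

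**What to change.** Keep the Day 141 to 196 summary as the stated Week 24 endpoint. In SAP 2.5.4, add an exception for WIWI, OSEP Part 2 and OSES Part 2, so that a form completed at a premature end-of-treatment visit is retained whatever its study day.

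Then present, by approach group, one supplementary table or listing that uses the Week 24 form if there is one and otherwise the premature form with its study day. State how many patients in each group have only a premature form. With 15 patients a listing may be enough.

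The cost is a short addition to the SAP and one output, with no new data collection. The small downside is that the supplementary summary mixes ratings made after different lengths of participation, which is why the study day should be shown and the Week 24 result kept beside it.
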